A.4	R code for secondary quantitative outcome S3	24

1 Statistical analysis plan approval signature page

Person writing the SAP:

Name: [name]

Position/Title: Associate Professor in Biostatistics

[figure not shown]
January 13, 2025

Signature & Date

Approved by:

Name: [name]

Position/Title: MD PhD, Senior Consultant

January 15, 2025

Signature & Date

Name: [name]

Position/Title: MD, PhD, Associate Professor, Senior Consultant

15-01-2025

Signature & Date

2 List of Abbreviations

- ALL: Acute Lymphoblastic Leukemia
- AML: Acute Myeloid Leukemia
- ANC: Absolute Neutrophil Count
- ANCOVA: Analysis of covariance
- CI: Confidence Interval
- GEE: Generalized Estimating Equations
- ITT: Intention-To-Treat
- SAE: Severe adverse event
- SAP: Statistical Analysis Plan

3 Introduction

This document is the statistical analysis plan (SAP) for an open label, investigator-initiated, parallel group, 1:1 randomized, multicenter, clinical trial of “short” versus “standard” (i.e., “long”) empirical antibiotics treatment duration of febrile neutropenia in high-risk children with cancer. Included children have an absolute neutrophil count (ANC) $< 0.5 \times 10^9$ cells/L and an expected duration of neutropenia of more than seven days. The primary endpoint is the number of days without antibiotic treatment within the first 28 days after treatment initiation. It is hypothesized that a “short” empirical antibiotics treatment duration is sufficient to prevent reinfection that would require additional antibiotic treatment days, hence superior to “standard” treatment duration. Randomization was stratified by site, via block randomization with random block size. Patient accrual has stopped early because of lower accrual rate than anticipated, as detailed in Sec. 3.1.

This SAP has been written after this decision to stop the trial early was taken. The changes to the protocol-planned analyses are summarized in Section 12. We do not consider them as major changes and the rationale for each of them is provided.

3.1 Early termination of the trial

The study had a lower accrual rate than anticipated, presumably for two reasons. First, the COVID-19 lockdown and restrictions in Denmark led to fewer leukemia diagnoses and fewer febrile episodes among the patients. Second, changes in standard cancer treatment protocols resulted in shorter neutropenia periods. This resulted in fewer patients fulfilling the inclusion criteria at the study sites.

Initially, the study period was extended by one year within the available funds (2020–2022 → 2020–2023). On November 8th, 2023, a meeting with the study board ([name]) was held. By that time, around 80 episodes had been included. It was decided to extend the study by another year, continuing through 2024, with recruitment ending on December 31st, 2024. Although the target of 220 episodes would not be reached, the sample size was estimated sufficiently large to provide valuable findings. Additionally, an opportunity to pool the data of this trial with

similar data from an Australian study group came up. It is anticipated that a meta-analysis of the two trials will be performed and that it will mitigate the limitations of the reduced sample size. Extending the study to reach the initially planned 220 episodes was estimated to require another five years, which would have led to funding difficulties. Additionally, the decline in the inclusion rate reflects a change in the patient population over time and this would have complicated the interpretation of the results, had the study been further extended.

4 Objectives, Endpoints, and Estimands

4.1 Primary objective, endpoint and estimand

The two treatment strategies (interventions) being investigated are the following.

- **Experimental (“short”):** discontinuation of antibiotics, despite neutrophil count $< 0.5 \times 10^9$ cells/L, after 48 hours of apyrexia and clinical stability. A child is considered clinically stable by the treating physician when there is resolution of all symptoms and signs of infection, and normalization of vital signs including heart rate, respiratory rate, oxygen saturation, blood pressure, and daily diuresis.
- **Control (“standard” or “long”):** discontinuation of antibiotics when either i) neutrophil count is $\geq 0.5 \times 10^9$ cells/L, and the child is afebrile and clinical stable or ii) the child has received 10 days of antibiotics and has been afebrile and clinically stable for 7 days.

The two treatment strategies are followed from randomization until neutrophil recovery (i.e. neutrophil count $\geq 0.5 \times 10^9$) or 28 days, whichever comes last. In case of relapsing fever, the patients continue to be treated according to the same treatment strategy (“short” or “long”). Randomization could occur from 36 hours after initiation of antibiotics until 48 hours of apyrexia and clinical stability (when the two treatment strategies can start to differ).

The primary outcome is the number of days without antibiotic treatment within the first 28 days after treatment initiation. For each of the 28 days, the information of whether the patient received antibiotics has been collected. The typical reasons for restarting antibiotics are new onset of fever, typically:

- febrile neutropenia (without documented infection)
- fever with or without neutropenia due to a possible or proven bacterial infection, including bacteremia (bacterial infection in the blood stream), pneumonia, skin infection, gastroenteritis or typhilitis (infection in the gut), urinary infection or other types of focal infections; side effects to chemotherapy that is accompanied by fever, such as pancreatitis

Restarting antibiotics might also happen without new onset of fever, for instance in case of suspicion of infection (e.g. focal symptoms from skin, lungs, gastrointestinal, etc).

The primary clinical question of interest is: *“Is the mean number of days alive without antibiotic treatment, within 28 days after treatment started, larger when children receive the “short” treatment duration strategy than when they receive the “long”, among children with cancer who started antibiotic treatment for high risk neutropenic fever of unknown origin, regardless of any intervention”*

during the follow-up needed to ensure good clinical care?

Accordingly, the primary estimand is described by the following attributes:

- Population: children (aged 0-17) with cancer receiving antibiotic treatment for high risk neutropenic fever of unknown origin 48 hours after presentation. In particular, children with
 - a single temperature of at least 38.5° C , or a temperature above 38.0° C sustained over a 1-hour period (auricular, oral or rectal), at presentation.
 - an absolute neutrophil count $< 0.5 \times 10^9$ cells/L and an expected duration of neutropenia of more than 7 days at presentation.
 - a negative blood culture (or other clinically relevant culture) 48h after the start of the culture.
- Endpoint: number of days alive without antibiotic treatment within the first 28 days after treatment initiation.
- Treatment: The investigational interventions (“short” vs “long”, as defined above) regardless of adherence and of any subsequent treatment decision or intervention during the follow-up needed to ensure good clinical care (“treatment policy strategy”, see [14]).
- The intercurrent event “any subsequent treatment decision or intervention needed to ensure good clinical care” is addressed by the treatment condition of interest attribute (“treatment policy strategy”, see [14]). The intercurrent event adherence to the investigational intervention is also addressed by the treatment condition of interest attribute (“treatment policy strategy”, see [14]). There are no other relevant intercurrent events anticipated.
- Population-level summary: Difference in means between treatment conditions.

Remarks:

- (i) The “treatment policy strategy” for the intercurrent event “adherence to the investigational intervention” is consistent with an Intention-To-Treat principle/analysis discussed in Section 5.1. In our context, “adherence” is defined as “continue antibiotic treatment” as long as defined by the treatment strategy (not shorter, not longer).
- (ii) It might happen that the blood culture (or other clinically relevant culture) turns positive late (after randomization), even though this is not expected to happen (or only in a few cases). If this happens, standard treatment that targets the newly identified cause of infection will be given identically in both arm. This is implicitly meant by the statement “regardless of any subsequent treatment decision or intervention during the follow-up needed to ensure good clinical care” in the treatment and intercurrent event attributes above.

4.2 Secondary endpoints

There are five secondary outcomes:

S1: Severe adverse event (SAE) within 28 days, defined as any of these events:

- Severe sepsis, defined as either (i) vasoactive treatment requirement or (ii) fluid bolus requirement $>20\text{mL/kg}$ or (iii) respiratory support requirement (mechanical ventilation).

- Fever with positive blood culture. For possible contaminants, at least two positive culture bottles were required. Possible contaminants include coagulase negative staphylococcus, micrococcus spp., non hemolytic streptococcus, Corynebacterium spp, Propionibacterium spp, Bacillus spp.
- Severe focal infection highly suspicious of bacterial cause, requiring antibiotic treatment (e.g. lungs, abdomen, CNS, skin)
- Death

S2: New episode of neutropenic fever within 28 days.

S3: Days alive without fever within 28 days.

S4: Mortality within 28 days.

S5: Time to bone marrow recovery (up to 3 month), defined as the time from start of treatment to first absolute neutrophil count (ANC) $\geq 0.5 \times 10^9$ cells/L.

Note: see Section 5.7 for details about the definitions of fever, neutropenia/neutropenic, **S2** and **S3**.

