4.3 Secondary objectives and estimands

For each of the secondary **binary** outcomes **S1**, **S2** and **S4**, the secondary objectives are to estimate the risks of the outcome in the two arms; as well as the risk differences. The corresponding clinical questions of interest are:

“What are the risks of [SAE / new episode of neutropenic fever / death] within 28 days after treatment started, when receiving the “short” and “long” treatment duration strategies, among children with cancer who started antibiotic treatment for high risk neutropenic fever of unknown origin, regardless of any intervention during the follow-up needed to ensure good clinical care? What is the corresponding risk [ratio / ratio / difference]?”

Accordingly, the corresponding estimands are defined as the primary estimands of Section 4.1, except for:

- the endpoint attributes, which are defined by the above items **S1**, **S2** and **S4**
- The intercurrent event “death within 28 days” does not exist for outcome **S4**. For **S1** and **S2**, it is implicitly addressed by the definition of the endpoint (as a classical competing event: in case death happens before the outcome of interest, the outcome of interest did not happen).
- Population-level summary: risk ratio for **S1** and **S2** and difference in risk for **S4** (between arms).

For each of the secondary **quantitative** outcomes **S3** and **S5**, the main secondary objectives are to estimate the medians of the outcome in the two arms; as well as their differences. The corresponding clinical questions of interest are:

“What are the median [number of day alive without fever within 28 days / time to bone marrow recovery], when receiving the “short” and “long” treatment duration strategies, among

children with cancer who started antibiotic treatment for high risk neutropenic fever of unknown origin, regardless of any intervention during the follow-up needed to ensure good clinical care? What is the corresponding risk difference?"

Accordingly, the corresponding estimands are defined as the primary estimands of Section 4.1, except for:

- the endpoint attributes, which are defined by the above items **S3** and **S5**

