5.7 Pivotal definitions

5.7.1 Time zero

To define many outcomes, e.g., **S2**: “new episode of neutropenic fever within 28 days”, we need to precisely define when the time starts. This is necessary to properly define the time window, e.g. “within 28 days”. In this SAP, we define that time (i.e., time zero) at the time of treatment initiation, not at time of randomization, which should occur appropriately 48 hours later. This is consistent with the definition of the primary outcome (see Section 4.1) and it should facilitate the interpretation of the results.

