8.1 Binary secondary endpoints

Secondary outcomes **S1**, **S2** and **S4** are binary. For **S1** and **S2**, we will first compute the logarithm of the risk ratio and its confidence interval using a GEE approach [17], again to account for a potential within-patient correlation. Unlike for the primary analysis, here we will use a log-linear model. Specifically, the variance and link functions that define the GEE will be that of a binary family with a log link. Here again, we will use an independent working correlation structure, for the same reasons mentioned above. To compute the point estimate of the risk ratio and its confidence interval, we will then exponentiate the fitted log of the risk ratio and its confidence interval. We will not adjust for baseline variables in this analysis, mainly for three reasons already mentioned in Section 5.6. First, non-linear models do not directly provide marginal effect estimates [10]. Second, the baseline covariates are not expected to be substantially prognostic of the outcomes and third, because of the limited (effective) sample size. An example of R code corresponding to this analysis is provided in appendix A.2.

For outcome **S4** (mortality), we expect very few events (if any), say less than 1% (so, ≤ 2 in the dataset). Hence we will use an exact method instead of a GEE approach, as the asymptotic approximations implicitly used by a GEE approach would be very questionable. The method will not account for the within patient correlation, as we are not aware of any exact method that could do that. But, this is a relatively minor limitation when the risks are very small. Specifically, we will use an exact unconditional test using the score statistic ordering as in Nielsen et al. [19], and implemented in the `uncondExact2x2()` function of the R package `exact2x2`; see [8] for the mathematical details and Appendix A.3 for the specific R code that we will use.

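### S1 counts events from antibiotic start, so severe sepsis before randomization enters both arms and moves the S1 risk ratio toward 1 by an amount the SAP does not let one know

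*SAP*

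**What the plan says.** Section 4.2 defines S1 as "Severe adverse event (SAE) within 28 days, defined as any of these events" and lists severe sepsis, fever with positive blood culture, severe focal infection and death. The sepsis item reads "Severe sepsis, defined as either (i) vasoactive treatment requirement or (ii) fluid bolus requirement" above a stated volume, or mechanical ventilation. The focal item reads "Severe focal infection highly suspicious of bacterial cause, requiring antibiotic treatment". Neither carries a timing condition, whereas S2, in the same list, is limited to a new episode.

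Section 5.7.1 fixes the clock: "In this SAP, we define that time (i.e., time zero) at the time of treatment initiation, not at time of randomization". Its reasons are consistency with the primary outcome and easier interpretation. Section 4.3 words the S1 question in the same way, as the risk "within 28 days after treatment started, when receiving the “short” and “long” treatment duration strategies", and names the risk ratio as the summary for S1.

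Section 4.1 allows randomization from 36 hours after antibiotic start "until 48 hours of apyrexia and clinical stability (when the two treatment strategies can start to differ"), and follows the strategies from randomization. For the analysis, section 8.1 says "we will first compute the logarithm of the risk ratio and its confidence interval using a GEE approach". It is unadjusted (section 5.6) and uses all randomized episodes (section 5.1). No section sets aside S1 events before randomization or plans an S1 analysis from randomization.

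**The concern.** Every episode has at least 36 hours inside the S1 window during which no strategy has been assigned, and more if fever persists. These are also the hours around presentation. A child who needs a large fluid bolus on day 0 and is randomized on day 3 is S1 = yes in either arm. Since S1 is one yes/no value per episode, a new serious event after antibiotics stop leaves that value unchanged.

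The stated reason for this time zero fits the primary outcome but does not carry over to S1. The primary summary is a difference in means, in which pre-randomization antibiotic days add the same expected amount to each arm and cancel. The S1 summary is a ratio, in which a common added risk does not cancel. For an outcome meant to show whether stopping antibiotics during neutropenia does harm, a shift toward 1 is the less cautious direction. The SAP also drops its earlier non-inferiority margin (section 12, item 3), so readers will judge S1 from the estimate and its interval alone.

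**Working it through.** **Which components can occur before randomization.**
- Death cannot, since the episode would not have been randomized.
- A culture positive by 48 hours conflicts with the population in section 4.1.
- Severe focal infection fits poorly with fever of unknown origin, so its exposure is limited.
- Severe sepsis is the clear case: section 4.1 lets randomization precede clinical stability, and nothing in the SAP removes an early bolus or vasoactive treatment from S1.

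**Inputs.** The SAP states no S1 risk, risk ratio or power, so it has no S1 figure to reproduce. Its only usable number is the expected total of about 100 episodes (section 11.2), or about 50 per arm. Everything else is assumed:
- q = share of randomized episodes with an S1 event before randomization, equal in expectation in both arms;
- p = S1 risk from randomization in each arm, taken to be the same whether or not the episode had an early event.

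**Formulas.**
- S1 risk as planned = q + (1 − q)p.
- Planned ratio = [q + (1 − q)p_short] / [q + (1 − q)p_long].
- Planned risk difference = (1 − q)(p_short − p_long).

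**Results for p_short = 20%, p_long = 10% (ratio 2.00 from randomization).** Example at q = 5%: (0.05 + 0.95 × 0.20) / (0.05 + 0.95 × 0.10) = 0.240 / 0.145 = 1.66.

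| q | Short | Long | Ratio | Difference (points) |
|---|---|---|---|---|
| 0 | 20.0% | 10.0% | 2.00 | 10.0 |
| 1% | 20.8% | 10.9% | 1.91 | 9.9 |
| 2% | 21.6% | 11.8% | 1.83 | 9.8 |
| 5% | 24.0% | 14.5% | 1.66 | 9.5 |
| 10% | 28.0% | 19.0% | 1.47 | 9.0 |

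**Other assumed risks, at q = 1%, 2%, 5% and 10%.**
- 10% v 5% (ratio 2.00): 1.83, 1.71, 1.49, 1.31.
- 15% v 10% (ratio 1.50): 1.45, 1.42, 1.33, 1.24.

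**Set against sampling error.** With 50 episodes per arm and clustering ignored, an observed 20% v 10% gives SE(log ratio) = sqrt(0.8/10 + 0.9/5) = sqrt(0.26) = 0.51, hence a 95% interval of about 0.74 to 5.43. At q = 5% (24.0% v 14.5%) the interval is about 0.72 to 3.81.

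**Added noise.** The SD of the risk difference is sqrt((0.16 + 0.09)/50) = 7.1 points at q = 0, sqrt((0.1824 + 0.1240)/50) = 7.8 points at q = 5%, and sqrt((0.2016 + 0.1539)/50) = 8.4 points at q = 10%.

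**The case against.** The choice is deliberate. Section 5.7.1 rejects randomization as time zero and says why, and section 4.3 defines the S1 question over the same window, so the planned ratio does estimate what the SAP says it estimates. That stands: this is not an internal contradiction. It does not settle the matter, because section 4.3 asks for risk under each strategy, and events before assignment carry no information on that.

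The size rests wholly on q, which may be 0, and the protocol, not shown here, may exclude some early events. This also stands.

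Part of the early picture will be visible anyway. Section 10.1.3 plots S1 from time 0, section 10.2.4 tabulates components per arm, and section 10.1.1 describes children with more than one event and separates event rates on antibiotics from rates soon after stopping. None of these gives a post-randomization risk ratio, but early and repeat events are not wholly hidden.

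A reader might infer that chance imbalance in early events adds a large error of its own. Taken alone, that imbalance has an SD of sqrt(2 × 0.05 × 0.95/50) = 4.4 points at q = 5% and 6.0 points at q = 10%. It is not added on top of the existing SD: the total rises only from 7.1 to 7.8 or 8.4 points, and the planned interval already reflects this.

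**Conclusion.** The point holds for the S1 risk ratio, chiefly through severe sepsis. Any q above 0 that is equal in both arms moves the ratio toward 1. Over assumed q of 1% to 10%, a ratio of 2.00 becomes 1.91 to 1.47 with risks of 20% v 10%, or 1.83 to 1.31 with risks of 10% v 5%. At q = 0 nothing changes. The risk difference shrinks only by the factor (1 − q).

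A reader might go further and infer that the plan will make a harmful strategy look safe. The documents do not support that. They give no S1 risks and no count of early events, S1 has no formal test (section 5.3), and at about 100 episodes the interval is far wider than the shift in the point estimate. Nor does the SAP call S1 its main safety comparison; it is the first of five secondary outcomes. What is supported is a dilution of known direction and unknown size, which a small change to the definition largely removes.

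**What to change.** In sections 4.2 and 5.7.1, state that S1 is the first qualifying event with onset after randomization and up to day 28, and that an event already under way at randomization counts as pre-randomization. Align the S1 question in section 4.3. Apply the definition to the risk ratio (8.1), the cumulative incidence plot (10.1.3) and the component table (10.2.4). Report pre-randomization events per arm with the baseline characteristics (10.2.2), and keep S1 from antibiotic start as a sensitivity analysis.

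The cost is about one sentence in the definition and one re-derivation of S1. The timing data should exist, because section 10.1.1 needs event times and section 10.2.2 lists durations up to randomization. The downsides are somewhat fewer events, a wider interval, and a start of counting that differs from the primary outcome. Some dilution remains from events between randomization and the point at which the strategies can differ; the report should say so.

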4.3 Secondary objectives and estimands

For each of the secondary **binary** outcomes **S1**, **S2** and **S4**, the secondary objectives are to estimate the risks of the outcome in the two arms; as well as the risk differences. The corresponding clinical questions of interest are:

“What are the risks of [SAE / new episode of neutropenic fever / death] within 28 days after treatment started, when receiving the “short” and “long” treatment duration strategies, among children with cancer who started antibiotic treatment for high risk neutropenic fever of unknown origin, regardless of any intervention during the follow-up needed to ensure good clinical care? What is the corresponding risk [ratio / ratio / difference]?”

Accordingly, the corresponding estimands are defined as the primary estimands of Section 4.1, except for:

- the endpoint attributes, which are defined by the above items **S1**, **S2** and **S4**
- The intercurrent event “death within 28 days” does not exist for outcome **S4**. For **S1** and **S2**, it is implicitly addressed by the definition of the endpoint (as a classical competing event: in case death happens before the outcome of interest, the outcome of interest did not happen).
- Population-level summary: risk ratio for **S1** and **S2** and difference in risk for **S4** (between arms).

For each of the secondary **quantitative** outcomes **S3** and **S5**, the main secondary objectives are to estimate the medians of the outcome in the two arms; as well as their differences. The corresponding clinical questions of interest are:

“What are the median [number of day alive without fever within 28 days / time to bone marrow recovery], when receiving the “short” and “long” treatment duration strategies, among

children with cancer who started antibiotic treatment for high risk neutropenic fever of unknown origin, regardless of any intervention during the follow-up needed to ensure good clinical care? What is the corresponding risk difference?"

Accordingly, the corresponding estimands are defined as the primary estimands of Section 4.1, except for:

- the endpoint attributes, which are defined by the above items **S3** and **S5**
- with **S5**, the intercurrent event “death within 28 days” is implicitly addressed by the definition of the endpoint as a classical competing event: in case death happens before the outcome of interest, the outcome of interest did not happen and the time to bone marrow recovery is set to infinity to define the median time (see e.g. [20, 2]).
- Population-level summary: Difference in median between arms.

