5.3 Multiplicity Adjustment

No multiple testing correction will be used, as formal hypothesis testing will be performed only for the primary estimands described in Section 4.1. Reporting for other endpoints/estimands will be limited to point estimates of effects with 95% (two-sided) confidence intervals. The widths of the intervals will not be adjusted for multiplicity and therefore it will not be possible to use them in place of formal hypothesis testing. This is in line with common recommendations [18].

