# fit model
library(geepack)
geePrimary <- geeglm(days~ treat + age + age5 + age12
                      + cancer + anc + thrombo + thrombo50 +
                      thrombo100 + site,
                      data=d,                                # data set (long format)
                      id=id,                                 # patient ID (clusters)
                      family=gaussian("identity"), # usual linear model parametrization
                      corstr="independence")      # independent working correlation structure
summary(geePrimary)

```

In the above, the dataset "d" is assumed to include the following variables: "days" indicates the number of days alive without antibiotic treatment within the first 28 days, "id" the patient ID (clustering variable), "treat" the randomized treatment strategy, "age" the age at randomization, "cancer" the type of cancer, "anc" the absolute neutrophil count at presentation, "thrombo" the thrombocyte count at presentation and "site" the study site.

A.2 R code for secondary binary outcomes S1 and S2 analysis

```
library(geepack)
geeBinary <- geeglm(Y~treat,
                      data=d,
                      id=id,
                      family=binomial("log"),
                      corstr="independence")
#--- extract estimate and SE (log-scale) -----
logRR <- summary(geeBinary)$coef["treat","Estimate"]
SElogRR <- summary(geeBinary)$coef["treat","Std.err"]
#--- compute Risk Ratio and 95% CI -----
Results <- exp(c(logRR,
                  logRR-qnorm(0.975)*SElogRR,
                  logRR+qnorm(0.975)*SElogRR))
```

In the above, the variable "Y" indicates the binary outcome of interest, "id" the patient ID (clustering variable) and "treat" the randomized treatment strategy.

A.3 R code for mortality analysis (S4)

```
library(exact2x2)
uncondExact2x2(x1=x1obs,
                n1=n1obs,
                x2=x2obs,
                n2=n2obs,
                parmytype="difference", # estimand is risk difference
                alternative = "two.sided", # two-sided CI wanted
                method="score", # score statistic ordering is used
                conf.level = 0.95, # 95% confidence level
                conf.int=TRUE) # computation of CI wanted
```

A.4 R code for secondary quantitative outcome S3

In the R code below, we assume that the dataset R contains the following variables:

- days: the outcome, a number of days corresponding to either S3 or S5.

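### Does the SAP set a risk-difference objective for S1 and S2 and then fail to plan an estimate of it?

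*SAP*

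**What the plan says.** Section 4.3 names the effect measure for the binary secondary outcomes three times.

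- The objective, for S1, S2 and S4 together: "the secondary objectives are to estimate the risks of the outcome in the two arms; as well as the risk differences".
- The clinical question, in the order S1, S2, S4: "What is the corresponding risk [ratio / ratio / difference".
- The estimand attribute: "Population-level summary: risk ratio for" S1 and S2, with a difference in risk kept for S4.

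Section 8.1 carries out the second and third of these. For S1 and S2, "we will first compute the logarithm of the risk ratio and its confidence interval using a GEE approach", with a log link, and the result is then exponentiated. Appendix A.2 returns the risk ratio and its 95% interval and nothing else. Appendix A.3 gives a risk difference with an interval, for S4 only.

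Three other places bear on the point. Section 5.3 says "Reporting for other endpoints/estimands will be limited to point estimates of effects with 95% (two-sided) confidence intervals". Section 10.1.3 plans the cumulative incidence of S1 and S2 per arm up to day 28, with pointwise 95% intervals from GEE. Section 10.2.5 summarises every outcome per arm.

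Section 4.3 also ends its question about the medians of S3 and S5 with "What is the corresponding risk difference", although their stated summary is "Population-level summary: Difference in median between arms".

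**The concern.** An objective should lead to an estimate. Taken alone, the first sentence of 4.3 promises an absolute contrast between arms for S1 and S2, and no section plans that contrast with an interval. Section 5.3 says that non-primary effects are reported as estimates with 95% intervals, so a reader could conclude that a stated objective has been left without its analysis.

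The outcomes matter. S1 and S2 bear directly on whether antibiotics can be stopped early without harm. A ratio alone does not show the absolute excess, and the SAP gives no expected risks for S1 or S2 from which to translate it. If the wording were a genuine open choice, the measure could be picked after the results were known.

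**Working it through.** **Which measure is pre-specified?**

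| Place in the SAP | S1 and S2 | S4 |
|---|---|---|
| 4.3, objective sentence | difference | difference |
| 4.3, clinical question | ratio | difference |
| 4.3, population-level summary | ratio | difference |
| 8.1, method | ratio (log-link GEE) | exact method |
| A.2 / A.3, code | ratio | difference |

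The objective sentence is the only outlier. The population-level summary is the attribute that defines the estimand, and the method and code match it. Section 4.3 makes a similar slip over S3 and S5, calling a contrast of medians a risk difference, which also points to loose drafting. Section 5.3 is met: the estimand for S1 and S2 is the ratio, and the ratio gets an estimate and an interval.

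**Is the absolute effect lost?** The A.2 model has only a treatment term and an independence working correlation, so its fitted arm risks are the observed proportions. The ratio and the difference come from the same two numbers, which 10.1.3 and 10.2.5 also report. What is not planned is an interval for the difference.

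**How much do the two measures differ?** The SAP states no figure for S1 or S2 to reproduce. Inputs: 50 episodes per arm (half of the roughly 100 anticipated in 11.2). Assumed: independent episodes, a risk ratio of 1.5, and a long-arm risk p0 of 10%, 20% or 30%, with p1 = 1.5 × p0.

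- Difference: (p1 − p0) ± 1.96 × √[p1(1 − p1)/50 + p0(1 − p0)/50]
- Ratio: 1.5 × exp(± 1.96 × √[(1 − p1)/(50 p1) + (1 − p0)/(50 p0)])

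| p0 | p1 | Difference, points (95% CI) | Ratio (95% CI) |
|---|---|---|---|
| 10% | 15% | 5 (−7.9 to 17.9) | 1.5 (0.52 to 4.34) |
| 20% | 30% | 10 (−6.9 to 26.9) | 1.5 (0.75 to 3.01) |
| 30% | 45% | 15 (−3.7 to 33.7) | 1.5 (0.89 to 2.53) |

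One ratio fits several differences, as in any trial that reports a ratio. In each row both intervals include no effect.

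**Can a reader recover an interval for the difference?** Take the 20% row. The arm half-widths are 1.96 × √(0.16/50) = 0.111 and 1.96 × √(0.21/50) = 0.127. Combined, √(0.111² + 0.127²) = 0.169, that is 10 ± 16.9 points, the interval in the table.

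This ignores covariance between arms from children randomized more than once. Assume 25 patients with two episodes each, giving 12.5 same-arm and 12.5 opposite-arm pairs on average, and within-patient correlation ρ. In units of √[p(1 − p)]:

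- variance from the two arms separately: 0.04 + 2 × 12.5ρ/2500 = 0.04 + 0.01ρ
- joint variance: 0.04 + 0.01ρ − 0.01ρ = 0.04
- ratio of standard errors, √[(0.04 + 0.01ρ)/0.04]: 1.012, 1.025 and 1.061 for ρ = 0.1, 0.2 and 0.5

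The recovered interval is thus 1% to 6% too wide. If all 25 pairs were in opposite arms, the ratio would be √[0.04/(0.04 − 0.02ρ)], which is 1.026 at ρ = 0.1 and 1.155 at ρ = 0.5. With positive correlation the error is towards caution.

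**The case for a change.** The best case for a change is that S1 and S2 carry the safety message. Section 12, item 3, drops the earlier 10% non-inferiority margin, and 5.3 allows no formal test outside the primary outcome, so the safety reading rests entirely on estimates and intervals. An absolute excess is what clinicians and families weigh, and it cannot be read from the ratio alone. One extra identity-link GEE call would supply a cluster-robust interval, and fixing it in advance would stop it being chosen after the results are seen.

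The inconsistency in 4.3 stands, and so does the usefulness of an absolute measure beside a ratio. But a supporting measure that a reviewer would welcome is not the repair of a wrong result. The arm risks with intervals already let the reader see the absolute scale, and the gain in precision is modest. The addition also has a cost: section 9 analyses E2 in the same way as S2, and 10.1.4 repeats the section 8 analyses in the subgroup with ANC at or below 0.1 × 10⁹ cells/L, so further unadjusted intervals would appear there too. The risk of a choice made after the results is small, because the estimand, method and code already agree on the ratio.

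**Conclusion.** The objective sentence in 4.3 is a clerical slip, as is the closing phrase of the S3 and S5 question. The risk ratio is unambiguously the pre-specified estimand for S1 and S2, the difference is the estimand for S4, and the planned analyses deliver both with intervals. The text could be tidied at any convenient revision, but that would change no result, and nothing depends on it.

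What is unplanned is an interval for the S1 and S2 risk differences. Their point values follow from the planned arm risks, and an approximate interval follows from the arm intervals, about 1% to 6% too wide under the main assumptions (up to about 15% if every repeat pair fell in opposite arms with correlation 0.5). These sizes rest on an assumed 50 episodes per arm, 25 patients with two episodes, and assumed risks and correlations, none of which the SAP gives for S1 or S2. The reading of the estimand rests on the text alone.
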